7.5.2.2 Liver Enzymes and Total Bilirubin

The following potentially clinically significant criteria for liver tests – defined as Alkaline Phosphatase (ALP), Alanine Transaminase (ALT), total bilirubin, Aspartate Transaminase (AST) and their combination are defined. The subject's highest value during the study period will be used.

Parameter	Criteria
ALT	> 3xULN
	> 5xULN
	> 10xULN
	>20xULN
AST	> 3xULN
	> 5xULN
	> 10xULN
	>20xULN
ALT or AST	> 3xULN
	> 5xULN
	> 10xULN
	>20xULN
Total Bilirubin	>2xULN
Alkaline Phosphatase	> 1.5xULN
ALT and/or AST AND Total Bilirubin [1]	ALT and/or AST > 3xULN AND Total Bilirubin > 2xULN
ALT and/or AST AND Alkaline Phosphatase AND Total Bilirubin [1]	ALT and/or AST > 3xULN AND Alkaline Phosphatase < 2xULN AND Total Bilirubin > 2xULN

[1] Combination of values measured within same day or within 1 day apart

The number and percentage of subjects with potentially clinically significant values in liver enzyme and total bilirubin tests during the study period will be presented.

7.5.3 Vital Signs

Descriptive statistics for vital signs (systolic blood pressure, diastolic blood pressure, pulse and body temperature) and weight will be presented at each visit (See Section 7.11.3).

Additionally, a within-subject change will be calculated per visit as the postbaseline measurement minus the baseline measurement and summarized in the same way.

The following data will be presented graphically:

- Vital sign results (actual values) using box plot
- Vital sign results x study days (relative days from administration of the study drug) using spaghetti plot

7.6 Analysis of PK

Not Applicable.

7.7 Analysis of PD

Not Applicable.

7.8 Subgroups of Interest

Not Applicable.

7.9 Other Analyses

Not Applicable.

7.10 Interim Analysis (and Early Discontinuation of the Clinical Study)

An interim assessment will be conducted at 6 months from first subject enrollment, with respect to safety. The report will be submitted to the health authority.

7.11 Handling of Missing Data, Outliers, Visit Windows, and Other Information

7.11.1 Missing Data

As a general principle, missing data will not be imputed, except for the following exceptions.

The partial missing start/end dates of AE (Adverse Events), CM (Prior and Concomitant Prostate Cancer Medications, Concomitant Medications, Non-Medication Therapy), MH (Medical History, Primary Diagnosis), and PR (Radiation for Prostate Cancer, Procedures for Prostate Cancer) will be imputed as below.

- If the start day and/or month is unknown, the day and/or month will be imputed by 1st and January, respectively. In case of AE with onset after first dose of study drug, use the imputed date or the first dose date of study drug, whichever is later.
- If the end day and/or month is unknown, the day and/or month will be imputed by the last day of the month and December, respectively.

The imputed dates will be used to determine duration of disease at screening (See Section 6.3).

7.11.2 Outliers

All values will be included in the analyses.

	ior vitai Signs, Chincai La	
Analysis visit	Specified day	Allowed time window
Baseline	Day0001	Last nonmissing value before the first dose.
Day0029(Week5)	Day0029	Specified day \pm 7 days
Day0057(Week9)	Day0057	Specified day \pm 7 days
Day0085(Week13)	Day0085	Specified day \pm 7 days
Day0169(Week25)	Day0169	Specified day \pm 7 days
Day0253(Week37)	Day0253	Specified day \pm 7 days
Day0337(Week49)	Day0337	Specified day \pm 7 days
Day0421(Week61)	Day0421	Specified day \pm 7 days
Day0505(Week73)	Day0505	Specified day \pm 7 days
Day0589(Week85)	Day0589	Specified day \pm 7 days
Day0673(Week97)	Day0673	Specified day \pm 7 days
Day0757(Week109)	Day0757	Specified day \pm 7 days
Day0841(Week121)	Day0841	Specified day \pm 7 days
Day0925(Week133)	Day0925	Specified day \pm 7 days
Day1009(Week145)	Day1009	Specified day \pm 7 days
Day1093(Week157)	Day1093	Specified day \pm 7 days
Day1177(Week169)	Day1177	Specified day \pm 7 days
Day1261(Week181)	Day1261	Specified day \pm 7 days
Day1345(Week193)	Day1345	Specified day \pm 7 days
Day1429(Week205)	Day1429	Specified day \pm 7 days
Safety Follow-up	30 days after Last Dose	Specified day \pm 7 days

7.11.3 Visit Window for Vital Signs, Clinical Labs and PSA

As for the analysis visits of Day XXXX (Week XXX), the values measured on or before withdrawal day will be accepted for discontinued subjects. The value which assessment day is the closest to the defined specified day within this window is used. If two values are equally close, the latter is used in the analysis.

Version	Date	Changes	Comment/rationale for change
1.0	3-Jun-2019	NA	Document finalized
2.0	25-Jan-2021	Protocol DeviationsTo include the analysis of protocol deviations according to the change quality documents.	
3.0	26-Feb-2024	GeneralConsiderationsRemoved dictionaryversion of MedDRA andWHODDE.	To comply with the Statistical Analysis Plan template.
		Visit Window for Vital Signs, Clinical Labs and PSA Updated time windows for visit increase.	To address visit increase.
		Missing Data Updated imputation for partial missing start/end dates of AE, CM, MH, PR.	To address partial missing dates.
		FLOW CHART AND VISIT SCHEDULE Removed the flow chart and visit schedule and changed to refer to the protocol.	To follow the contents of latest Statistical Analysis Plan format.
		General Considerations Updated SAS version.	

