Adverse events (AEs) will be coded using the Medical Dictionary for Regulatory Activities (MedDRA). The number and percentage of subjects with treatment-emergent AEs, serious AEs (SAEs), AEs leading to withdrawal of treatment, and AEs possibly related to the study drug will be calculated. Changes in laboratory parameters, vital signs, and weight over time will be tabulated. **Efficacy:**

The PSA response rate will be summarized by time point.

Pharmacokinetics:

Not applicable

Pharmacodynamics:

Not applicable

Interim analyses:

An interim assessment will be conducted at 6 month from first subject enrollment, with respect to safety. The report will be submitted to the health authority.

V. FLOW CHART AND SCHEDULE OF ASSESSMENTS

Flow Chart

Study Day	Screening Visit	1	29	57	85	169 & every subsequent 84 days	Safety Follow-up	Unscheduled
Study Week	-4 to -1 (28 Days)	1	5	9	13	25	30 Days after Last Dose§	Visit†
Window (Days)			± 7	± 7	± 7	± 7	± 7	NA
Informed Consent	Х							
Medical History	Х							
Inclusion/Exclusion Criteria	Х	Х						
IRT		Х						
Vital Signs	Х	Х	Х	Х	Х	Х	Х	Х
Physical Examination including Weight¶	Х	Х	Х	Х	Х	Х	Х	Х
Height	Х							
Clinical Labs ‡	Х	Х	Х	Х	Х	Х	Х	Х
PSA	Х	Х	Х	Х	X	Х	Х	
ECOG Performance Status	Х							
Adverse Events§§	Х	Х	Х	X	X	Х	Х	Х
Previous and Concomitant Medications	X	Х	Х	Х	Х	X	Х	Х
Study Drug Dispensing		Х	Х	Х	X	Х		
Study Drug Treatment		Х	Х	X	Х	Х		

Table 1: Schedule of Assessments

ECOG: Eastern Cooperative Oncology Group; IRT: Interactive Response Technology; NA: not applicable; PSA: prostate-specific antigen

- [†] Unscheduled visits may be performed at any time during the study whenever necessary to assess for or follow-up on adverse events at the subject's request or if deemed necessary by the Investigator. Procedures and assessments are to be performed as clinically indicated.
- § Or prior to initiation of an investigational agent or new therapy for prostate cancer, whichever occurs first.
- A brief physical examination is required at each visit, with the exception of the screening visit during which a complete physical examination will be completed.
- ‡ Laboratory assessments include serum chemistries and hematology.

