3.2 Study Design

This study is a multicenter phase 4, open-label, single-arm, safety and efficacy study of enzalutamide (160 mg/day) in patients with progressive mCRPC who have previously been treated with docetaxel-based chemotherapy. Approximately 50 patients will be enrolled and treated with enzalutamide 160 mg once daily until study discontinuation criteria is met.

Safety and tolerability will be assessed by the collection of adverse events, vital signs, physical examinations and safety laboratory evaluations.

PSA will be collected for assessment of prostate cancer status on Screening Visit, Days 1, 29, 57, 85, 169, every subsequent 84 days and Safety Follow-up Visit.

Subjects will have a safety follow-up visit 30 days after their last dose of study drug or prior to initiation of another investigational agent or new therapy including commercial enzalutamide for prostate cancer, whichever occurs first.

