7.5.2 Clinical Laboratory Evaluation

7.5.2.1 All Laboratory Tests

Descriptive statistics for quantitative clinical laboratory variables, i.e. hematology and biochemistry will be presented at each visit (See Section 7.11.3). Additionally, a withinsubject change will be calculated as the postbaseline measurement minus the baseline measurement and summarized in the same way. Each laboratory result will be classified as low (L), normal (N), or high (H) at each visit according to the laboratory supplied reference ranges. The number and percentage of subjects below and above reference range will be summarized using shift table (from baseline to postbaseline).

The following data will be presented for quantitative clinical laboratory variables graphically:

- Laboratory test results (actual values) using box plot
- Laboratory test results x study days (relative days from administration of the study drug) using spaghetti plot

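### With one value per visit inside ±7 days, no table counts subjects by their worst hematology or non-liver chemistry result

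*SAP*

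**What the plan says.** The visit schedule in SAP 3.2 is "Days 1, 29, 57, 85, 169, every subsequent 84 days and Safety Follow-up Visit". The window table in SAP section 7.11 gives every post-baseline analysis visit, up to Day 1429 and then Safety Follow-up, a window of 7 days either side of the target. SAP 7.11.3 sets the selection rule: "The value which assessment day is the closest to the defined specified day within this window is used", with the later value taken on a tie. The rule does not separate scheduled from unscheduled samples, and nothing says where a value between windows goes.

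SAP 7.5.2.1 builds the laboratory tables on these visits. "Descriptive statistics for quantitative clinical laboratory variables, i.e. hematology and biochemistry will be presented at each visit (See Section 7.11.3"), and "Each laboratory result will be classified as low (L), normal (N), or high (H) at each visit". It then adds: "The number and percentage of subjects below and above reference range will be summarized using shift table (from baseline to postbaseline"). Protocol 7.5.2 plans shifts from baseline to each time point in the treatment period.

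Under the protocol's schedule of assessments (Table 1), "Unscheduled visits may be performed at any time during the study whenever necessary to assess for or follow-up on adverse events", and clinical laboratory tests are marked for those visits.

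SAP 7.5.2.2 summarizes ALT, AST, ALP and total bilirubin by each subject's highest value in the study period. No matching table is planned for hematology or the other chemistry tests.

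**The concern.** Unscheduled samples are taken because something may be wrong, so they are more likely than routine samples to be abnormal. A rule that keeps only the result nearest a fixed day tends to leave such samples out, either because they fall between windows or because a routine sample lies nearer the target. For neutrophils, platelets and non-liver chemistry, a subject with a low or high result between visits can then be counted as normal at every visit in the shift table.

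This matters because safety laboratory tests are a primary endpoint (protocol 2.3.1, SAP 6.2). Protocol 1.4 lists decreased neutrophil count among the important identified risks, and SAP 6.2 makes both that and thrombocytopenia adverse events of special interest.

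**Working it through.** The plan states no coverage figure to reproduce, so the days can be counted directly.

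**Inputs**
- Window width (SAP window table): 7 + 1 + 7 = 15 days.
- On-treatment analysis visits (SAP window table): Days 29, 57 and 85, then every 84 days from 169 to 1429. That is 3 + [(1429 − 169)/84 + 1] = 3 + 16 = 19 visits.
- Post-baseline days are counted from Day 2. The last on-treatment window closes on Day 1429 + 7 = 1436.

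**Formula.** Share of days in no window = 1 − (15 × number of windows closed by the end of follow-up) / (last day − 1).

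| Follow-up to | Windows | Days covered | Days counted | In no window |
|---|---|---|---|---|
| Day 92 | 3 | 45 | 91 | 50.5% |
| Day 176 | 4 | 60 | 175 | 65.7% |
| Day 365 | 6 | 90 | 364 | 75.3% |
| Day 1436 | 19 | 285 | 1,435 | 80.1% |

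Within one 84-day interval the share is 1 − 15/84 = 82.1%; within one 28-day interval it is 1 − 15/28 = 46.4%.

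**How the rule acts on single results (hypothetical days)**
- A visit or unscheduled sample on Day 95: the Day 85 window is Days 78 to 92 and the Day 169 window is Days 162 to 176. The result belongs to neither.
- A routine sample on Day 85 and an unscheduled one on Day 89: the distances are 0 and 4 days. The Day 89 result is dropped although it is in window.
- An unscheduled sample on Day 87 with the routine sample on Day 90: the distances are 2 and 5 days. The unscheduled result is used and the routine one dropped.

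**Early safety follow-up.** Protocol 2.2.1 places this visit 30 days after last dose, or before new therapy if that comes first. The SAP window is 30 ± 7, or days 23 to 37 after last dose. A compliant follow-up visit held, say, 10 days after last dose misses it. SAP 7.11.3 accepts numbered-day values in discontinued subjects only up to the withdrawal day, so this result appears to have no analysis visit.

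**The case against.** The strongest reply is that little reportable information is lost. The ±7-day analysis window equals the protocol visit window, so every on-treatment visit held on time is captured. Unscheduled results are not barred; one that is in window and closest is used. Liver tests have their highest-value table with no visit window stated. Spaghetti plots use actual study day, and laboratory data are listed. Abnormal results judged clinically significant are reported as adverse events, graded, and counted by preferred term and special-interest category whatever their day. The study is descriptive, single-arm and has about 50 subjects.

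Most of this stands, and it rules out two readings that a reader might infer. One is that about 80% of the data is discarded. That figure is a share of days at the longest follow-up, and the documents give neither the treatment duration nor the number of unscheduled samples. The other is that toxicity results vanish from all summaries; they leave only the by-visit and shift tables.

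The reply does not close the gap. Plots and listings give no count of subjects. The adverse-event route depends on the investigator finding the result clinically significant and either unrelated to the underlying disease or more severe than expected (protocol 5.5.1.1), so it does not replace an objective count.

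It is also fair to say that the shift sentence in SAP 7.5.2.1 does not itself cite the windows. The per-visit reading rests on the sentence before it and on protocol 7.5.2. SAP 7.11.2 keeps all values in the analyses, but under the heading of outliers, and it assigns no value to a visit.

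**Conclusion.** The gap is real but limited. For hematology and non-liver chemistry, results from late visits and between-window unscheduled visits, and in-window results that are not closest, do not reach the by-visit or shift tables. No table counts subjects by worst value for these tests. The likely direction is an understatement of laboratory abnormality in the shift tables. Its size cannot be estimated, because the documents give neither the number of unscheduled samples nor how far visits stray from their target days. The 51% to 80% range describes only how much of the calendar lies outside any window.

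The conclusion assumes that the shift table is built per visit. If the sponsor intends it to use all post-baseline results, the SAP should say so.

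A reader might extend the point to the PSA endpoint. The documents do not support that for confirmed PSA response, which uses the lowest post-baseline value and does not refer to the windows. Only the by-visit PSA summary is windowed, and since PSA is not marked for unscheduled visits, the issue there is late or early visits alone.

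**What to change.** 1. In SAP 7.5.2.1, add a shift table from baseline to worst post-baseline value, lowest and highest as relevant to the test, for all hematology and chemistry tests. Use every result after first dose, scheduled or unscheduled, through the safety follow-up visit including its +7 days. A cutoff at exactly 30 days after last dose would drop compliant follow-up samples from days 31 to 37.
2. In SAP 7.11.3, assign a safety follow-up visit held early, before new therapy, to the Safety Follow-up analysis visit.
3. State in SAP 7.11 how the outlier rule that retains all values fits with the one-value-per-visit rule.

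The by-visit windows may stay as they are. Contiguous windows cut midway between visits would leave no uncovered on-treatment day, but they are optional. They would let a value up to about 42 days (84/2) off target stand for a visit and, where the routine sample is missing, bring event-triggered results into the by-visit means. They would also still miss peaks, because one value per visit is kept.

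The cost is SAP wording and one extra table, with no new data. The table may show more abnormal values, and because it takes the worst of all samples it partly reflects how often each subject was sampled; a footnote should say so. Protocol 7.8 leaves window handling open until hard lock.

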		Appendix 1: SIGNATURE Removed the list of key contributors.	
		Safety Variables Added AESI definition	To add AESI analysis.
		Adverse Events of Special Interest Added AESI analysis.	

8 DOCUMENT REVISION HISTORY

Version	Date	Changes	Comment/rationale for change
		An Overview of Adverse Events Removed AE subgroup analysis.	To remove AE subgroup analysis, which is not necessary in CSR analysis.
		Adverse Events by SOC and PT Removed AE subgroup analysis.	
		Subgroups of Interest Changed to "Not Applicable".	

9 **REFERENCES**

[figure not shown]
- ICH Harmonized Tripartite Guideline E 3. Structure and Content of Clinical Study Reports, November 1995. (www.ich.org; Guidelines; "Efficacy" Topics)
- ICH Harmonized Tripartite Guideline E 9. Statistical Principles for Clinical Trials, February 1998. (www.ich.org; Guidelines; "Efficacy" Topics)

